In REVISE, patient-important upper gastrointestinal bleeding occurred more frequently than clinically-important upper gastrointestinal bleeding. While studies have reported risk factors for clinically-important upper gastrointestinal bleeding [14], the risk factors for patient-important upper gastrointestinal bleeding, as defined by ICU survivors and family members, remain unknown. While some bleeding events confer an increased risk of death [15], most bleeding ICU patients do not die with or from gastrointestinal bleeding [11]. Dying is nonetheless a competing risk for bleeding, and dying is more common than bleeding. Thus, the primary objective of the current study is to identify risk factors for patient-important upper gastrointestinal bleeding among invasively ventilated critically ill adults, taking into account illness severity and the competing risk of death.

Materials and Methods

Risk Factor Analysis

This pre-planned secondary analysis of the REVISE trial data will be guided by this protocol. The inception cohort will comprise the 4,821 participants in the REVISE trial. These were critically ill patients who were receiving invasive mechanical ventilation patients in the ICU, who were expected to remain ventilated beyond the calendar day after randomization, and were without a clear indication or contraindication to pantoprazole [12,13].

We will use Cox proportional hazards regression analysis to assess the effect of candidate risk factors on the hazard rate of the primary outcome of time to patient-important upper gastrointestinal bleeding, considering the competing risk of death [16,17]. In REVISE, approximately 10 times as many patients died at 90-days than experienced upper gastrointestinal bleeding. The main analysis will then be a competing risk analysis for the competing risk of death [18]. The proportional hazards assumption (which states that the effects of the time-dependent variables remain stable over time) will be assessed and handled appropriately using time-varying effects [19]; alternative methods will be used if this is not satisfactory [20]. We will also assess collinearity of the independent variables (e.g., therapeutic anticoagulation and coagulopathy).

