A secondary analysis will be to determine risk factors for the secondary outcome of clinically-important upper gastrointestinal bleeding. We defined clinically-important upper gastrointestinal bleeding as the presence of overt bleeding (hematemesis, overt nasogastric bleeding, melena, or hematochezia) and at least one of the following within 24 hours in the absence of another cause: spontaneous decrease in invasively monitored mean arterial pressure or non-invasive systolic or diastolic blood pressure of 20 mmHg or more or an orthostatic increase in pulse rate of 20 beats/minute and a decrease in systolic blood pressure of 10 mmHg, with or without vasopressor initiation or increase; vasopressor initiation; a decrease in hemoglobin of ≥ 20 g/L in a 24-hour period or less; transfusion of ≥ 2 units of packed red blood cells within 24 hours of bleeding, or therapeutic intervention (e.g., angio-embolization, surgery or endoscopic treatment of bleeding) [12]. Each bleed was reviewed in duplicate by an adjudication committee, blinded to study drug, to determine whether the clinically-important upper gastrointestinal bleeding criteria were fulfilled [22].

Among 4,821 patients, 109 (2.2%) had an event which were adjudicated as clinically-important upper gastrointestinal bleeding, 5 of whom bled on the ward prompting ICU readmission. These 5 patients will be censored at ICU discharge, as daily data for the time-dependent risk factors were not collected beyond the index ICU admission.

Independent Variables:

Bleeding risk factors will include both baseline and time-dependent variables. Factors will draw on pathophysiologic rationale and prior literature. Given the number of patient-important upper gastrointestinal bleeds, we have taken into account the suitable number of independent variables to avoid an over-fitted model [23]. The same risk factors will be analyzed for the secondary outcome of clinically-important upper gastrointestinal bleeding as for the primary outcome of patient-important upper gastrointestinal bleeding.

Baseline Variables

- 1) APACHE II score (considered as a continuous variable)
- 2) Medical vs. surgical/trauma (considered as 2 categories)
- 3) Pantoprazole versus placebo as randomized (considered as 2 categories)

Time-dependent Variables

- 1) Respiratory failure, defined as receiving invasive mechanical ventilation (considered as 2 categories)

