- 2) Circulatory failure, defined as receiving inotropes or vasopressors (any dose of any of norepinephrine, epinephrine, phenylephrine, vasopressin, dopamine, dobutamine or milrinone) (considered as 2 categories)
- 3) Renal failure including acute kidney injury or end-stage renal disease, defined as receiving renal replacement therapy (any of intermittent hemodialysis [IHD], continuous renal replacement therapy [CRRT], sustained low efficiency dialysis [SLED] or peritoneal dialysis) (considered as 2 categories)
- 4) Enteral nutrition in mL/day (considered as a continuous variable)

- 5) Therapeutic anticoagulation, defined as therapeutic unfractionated heparin or low molecular weight heparin, fondaparinux, warfarin, non-vitamin K antagonist oral anticoagulants including anti-Xa inhibitors and direct thrombin inhibitors, and thrombolytic therapy (considered as 2 categories)
- 6) Coagulopathy, defined as international normalized ratio (INR) > 3.0 or prothrombin time (PTT) > 70 seconds (considered as 2 categories)
- 7) Severe thrombocytopenia, defined as platelet count $< 50 \times 10^9/L$ (considered as 2 categories)
- 8) Platelet aggregation inhibitors, defined as receipt of any of acetyl salicylic acid, clopidogrel, dipyridamole, ticlopidine, tirofiban, P2Y12 inhibitors, or non-steroidal anti-inflammatory drugs (considered as 2 categories)
- 9) Corticosteroids, defined as any corticosteroid drug or dose, either enteral or intravenous administration (considered as 2 categories)

Sensitivity Analyses

- 1) To evaluate the effect of the competing risk of death, we will conduct an analysis that does not consider the competing risk of death.
- 2) To evaluate the influence of risk factors more proximate to the bleed, we will evaluate all time-dependent risk factors defined as any time in the preceding 2 days, instead of the preceding 3 days.

Secondary Analyses

- 1) To evaluate risk factors for clinically-important upper gastrointestinal bleeding, we will repeat the same analysis [11].
- 2) To evaluate whether enteral nutrition attenuates the effect of pantoprazole on bleeding prevention compared to placebo, we will include an interaction term between pantoprazole vs. placebo and amount of enteral nutrition received [24,25].

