- 3) To evaluate whether certain baseline conditions are associated with patient-important upper gastrointestinal bleeding, we will include these variables in the main model one at a time: acute hepatic failure [26], traumatic brain injury [27] and female sex [28].

Missing Data

We anticipate little missing data except for 2 risk factors in patients with length of ICU stay greater than 2 weeks. Platelet aggregation inhibitors and corticosteroids were not collected from day 15 onwards 14 on the abbreviated trial case report form. For the primary analysis, if there are any patients remaining in the ICU after 2 weeks who received a platelet aggregation inhibitor on day 14, we will impute that it was continued until ICU discharge, except in the event of bleeding, assuming that the indication persisted over time (e.g., coronary artery disease). For the primary analysis, we will impute that if there are any patients receiving corticosteroid treatment on day 14, it was continued only to day 21, assuming the indication resolved (e.g., septic shock).

Results

We will report independent variables and other characteristics of participants with and without patient-important upper gastrointestinal bleeding using descriptive statistics, including means and standard deviations (or medians with interquartile ranges, if appropriate) for continuous data, and numbers with percentages for categorical data.

Figures we will present include the day of each bleed in the ICU, the concordance between patient-important gastrointestinal bleeding and clinically-important upper gastrointestinal bleeding, and the daily use of invasive ventilation and any enteral nutrition.

Regression results will be presented as adjusted hazard ratios with 95% confidence intervals and corresponding two-tailed p-values for the associations of each independent variable with the primary and secondary outcomes. The criterion for statistical significance will be set at alpha = 0.05. No corrections for multiple testing will be performed because of the exploratory nature of the analyses, but findings will be interpreted in light of confidence intervals and cautiously interpreted.

Discussion

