In this study, we will examine baseline and time-dependent risk factors for patient-important upper gastrointestinal bleeding, including the effect of pantoprazole versus placebo. Use of the REVISE trial database will build on risk factor analyses of clinically-important upper gastrointestinal bleeding from prior large trials [25,29].

Strengths of this study include the focus on an outcome developed by ICU survivors and relatives of ICU survivors or decedents. We will minimize the risk of over-fitted regression models caused by evaluation of many admitting diagnoses. Beyond assessing baseline characteristics, we will use Cox models to assess interventions and key laboratory values reflecting events and exposures over the ICU stay. Although proton-pump inhibitors for bleeding prophylaxis do not affect 90-day mortality overall as shown in a recent meta-analysis (RR 0.99 [95% CI, 0.93 to 1.05]) [30], within-trial subgroup analysis suggests a possible heterogeneity of treatment effect based on disease severity. Accordingly, the main analysis will address the competing risk of death and a sensitivity analysis will evaluate whether this impacts the results. In this contemporary database, half of the patients were randomized to no stress ulcer prophylaxis, enabling the evaluation of risk factors with and without stress ulcer prophylaxis. This study will address some issues proposed for future research on this topic [31], including evaluating the volume of enteral nutrition (e.g., trophic versus full feeding) and special populations (e.g., acute hepatic failure). Heterogeneous patients from 68 international centers will increase the generalizability of the results.

Limitations of this study include no information on some uncommon exposures in the REVISE trial (e.g., non-invasive ventilation) and on some rare conditions (e.g., admitting diagnosis of organ transplantation). To focus on events that consume healthcare resources, we will not address overt bleeding, which often resolves; if it evolves into patient-important or clinically-important upper gastrointestinal bleeding, these events will be included in this analysis. This study is not designed to construct or both construct and validate a prediction model, which requires a different design. All analyses such as these are subject to confounding, yielding information on association rather than causation, needing cautious interpretation.

Conclusions

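### Enteral nutrition enters as a single mL/day term with no planned check of its shape, so the slope alone cannot support a trophic-versus-full reading

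*Combined protocol and SAP*

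**What the plan says.** Under Time-dependent Variables, item 4 reads "Enteral nutrition in mL/day (considered as a continuous variable". The word linear is not used. However, the Results section promises an adjusted hazard ratio for each independent variable, and the Independent Variables section says "we have taken into account the suitable number of independent variables to avoid an over-fitted model". One linear term is the natural reading.

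The Risk Factor Analysis section plans two model checks:

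- Proportional hazards, an assumption "which states that the effects of the time-dependent variables remain stable over time". This concerns stability over follow-up, not shape over volume. The fallback to alternative methods belongs to this check.
- Collinearity: "We will also assess collinearity of the independent variables (e.g., therapeutic anticoagulation and coagulopathy".

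Neither sensitivity analysis changes the form of enteral nutrition. One ignores the competing risk of death and the other shortens the exposure window to 2 days. The planned treatment interaction again uses the amount received. Any enteral nutrition, as a yes/no quantity, appears only in a descriptive figure of daily use.

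The Discussion says the study will address open research issues, among them "evaluating the volume of enteral nutrition (e.g., trophic versus full feeding".

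**The concern.** A full-versus-trophic hazard ratio can be calculated from a per-mL slope, but it is valid only if the log hazard is linear from 0 mL upward. Unfed windows sit at the low end of the volume scale and help to set the slope. If bleeding risk differs mainly between fed and unfed patients, the model reports that difference as a volume effect. A significant mL/day coefficient could then be taken as evidence on trophic versus full feeding when volume has no association among fed patients.

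The Results section promises that "findings will be interpreted in light of confidence intervals and cautiously interpreted". That caution does not reach this problem, because a confidence interval around a linear slope does not show that the shape is wrong.

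**Working it through.** **Figures from the document.** 136/4,821 = 2.82%, which reproduces the stated 2.8%. Five ward bleeds are censored, leaving 136 − 5 = 131 primary events. For the secondary outcome, 109 − 5 = 104. Terms: 3 baseline + 9 time-dependent = 12.

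**Events per parameter.** Primary: 131/12 = 10.9, and 131/13 = 10.1 with one added term. Secondary: 104/12 = 8.7 and 104/13 = 8.0.

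**Method.** For large samples, the fitted slope b of a single Cox term solves

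Σ p·x·exp(bx) / Σ p·exp(bx) = Σ p·h·x / Σ p·h,

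where p is the exposure share, x the volume and h the true relative hazard. The right-hand side is the mean volume at events. The model sees only that mean.

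**Hand-checkable example (assumed inputs).** Volumes are 0, 500 and 1,500 mL with shares 0.3, 0.3 and 0.4.

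- Only being fed matters (h = 1, 0.5, 0.5): mean volume at events = (75 + 300)/0.65 = 577 mL. The slope implies a full-versus-trophic HR of 0.65; the truth is 1.00.
- Only full feeding matters (h = 1, 1, 0.5): mean = (150 + 300)/0.80 = 562.5 mL. The slope implies 0.62; the truth is 0.50.

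Two opposite truths give almost the same output.

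**Range over mixes (assumed inputs).** Trophic volume is uniform on 50–500 mL and full on 800–1,800 mL. The contrast is between band means, 1,300 − 275 = 1,025 mL, so the implied HR is exp(1,025·b). The truth is any-feeding HR 0.5 and full-versus-trophic HR 1.0, with 131 events and 1,500 simulated trials per row.

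| None/trophic/full, % | HR implied by one slope | One-slope trend p<0.05 | 95% CI for full vs trophic, indicator added |
|---|---|---|---|
| 5/35/60 | 0.88 | 14.3% | 0.72–1.40 |
| 10/35/55 | 0.80 | 31.4% | 0.70–1.42 |
| 20/30/50 | 0.71 | 62.8% | 0.68–1.48 |
| 30/25/45 | 0.66 | 78.8% | 0.65–1.55 |
| 40/20/40 | 0.63 | 87.1% | 0.61–1.64 |

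With the indicator added, the volume term is significant in 4.5–5.4% of trials, close to the nominal level. In every row the two-term interval still includes the misread value.

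**Milder truths, same mixes.**

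- Any-feeding HR 0.75: implied HR 0.83–0.96, significant in about 6–22%.
- Graded effect (trophic 0.70, full 0.50, so true contrast 0.50/0.70 = 0.71): implied HR 0.61–0.71, a small error.

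**What the two-term model can detect (131 events).**

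- Power for the indicator is about 54–77% at any-feeding HR 0.5 and 12–20% at HR 0.75.
- Power for a truly linear volume effect (HR 0.63 per 1,000 mL) falls from about 85–89% to 53–79%.
- Power for a full-only effect (HR 0.5) falls from about 92–96% to 71–93%. Here the indicator shows a spurious HR of about 1.1, significant in about 4–8%, so this form of non-linearity passes almost unnoticed.

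All these figures precede adjustment for other covariates and are therefore optimistic.

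**The case against.** **No planned statement is shown to be wrong.** A reader might infer that the plan contradicts its own objective. It does not. A mL/day term does evaluate volume; trophic versus full is an example in the Discussion, with no categories, cut-points or contrast prespecified. The harm arises only if the slope is later converted into that contrast. This stands and limits the weight of the point.

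**The size is assumed.** The feeding shares, volume bands and effects are not in the document. The largest distortions need both a strong any-feeding effect and 20–40% unfed. This also stands.

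**The exposure is a 3-day window, not a day.** Windows with no feeding at all may be rarer than unfed days. If days were independent, 20–40% unfed days would give 0.2³ = 0.8% to 0.4³ = 6.4% unfed windows; with strong persistence the share stays near 20–40%. The document does not settle which applies. Nor does it say how mL/day is summarised over the window: the any-time-in-3-days rule suits a yes/no factor, not a volume.

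**The planned figure helps.** The daily plot of any enteral nutrition will show roughly how common unfed days are. It does not test shape.

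**The remedy is partial.** An indicator beside mL/day tests only a jump at zero and keeps linearity among the fed. A reader might take it as a full linearity check or a needed correction of the main model; the power figures support neither.

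**APACHE II is treated the same way.** It too is continuous with no shape check. That is true, but the Discussion attaches no comparable contrast to it.

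**Conclusion.** The point holds as a low-cost improvement to an exploratory, associational analysis. The plan fits one term for feeding volume, on the natural reading linear, and checks proportional hazards and collinearity but not shape. The resulting slope cannot separate being fed from being fed more, so it cannot alone carry a trophic-versus-full conclusion.

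The size cannot be established from the document. Under the assumed mixes with any-feeding HR 0.5 and no volume effect among the fed, the misread HR is about 0.63–0.88. The distortion is small if few 3-day windows are unfed, if the any-feeding effect is weak, or if the effect is graded. It would be tempting to say that the volume result will be biased or falsely significant. The document does not support that, because the true shape and the unfed share are both unknown.

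**What to change.** Leave the 12-term main model unchanged. Add one exploratory analysis for the primary outcome, in the pattern already used under Secondary Analyses, item 3 ("we will include these variables in the main model one at a time"). Suggested text:

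> *In an exploratory analysis we will add to the main model an indicator for any enteral nutrition in the 3-day exposure window, beside mL/day summarised over the same window as [state: mean, maximum or latest value]. We will report both hazard ratios with 95% confidence intervals. This analysis separates feeding from volume; it is not a full check of linearity, because it assumes linearity among fed windows. The indicator extrapolates to 0 mL and will not be read as trophic versus none. A non-significant result for either term will not be read as absence of an effect.*

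The cost is one paragraph and one parameter: 10.1 events per parameter instead of 10.9, the same model size as the one-at-a-time additions already planned. Repeating it for the secondary outcome would give 8.0 instead of 8.7. The plan should also state the limits shown above: lower power for volume, modest to poor power for the indicator, and a volume interval wide enough to include the misread value. The planned figure of any enteral nutrition suggests that the data are already available.

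If the analysis is not added, describe the Discussion's volume result as a linear trend only and draw no trophic-versus-full conclusion from it. That costs one sentence.

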4 Department of Critical Care, Université de Sherbrooke, Sherbrooke, Québec, Canada

5 Interdepartmental Division of Critical Care, University of Toronto, Toronto, Ontario, Canada

6 Department of Health Research Methods, Evidence and Impact, the Research Institute of St Joseph's Healthcare, Hamilton, Ontario, Canada

7 Departments of Medicine, Health Research Methods, Evidence and Impact, McMaster University, Hamilton, Ontario, Canada

Correspondence: [name], Departments of Medicine & Health Research Methods, Evidence and Impact, McMaster University Health Sciences Center, [name]; [contact]

Key Words: upper gastrointestinal bleeding, critically ill patient, risk factors, competing events

Word Count: 2051

Abstract Word Count: 262

REVISE: Clinical Trial Registration: www.clinicaltrials.gov NCT03374800

Abstract

Background: While studies have reported risk factors for clinically-important upper gastrointestinal bleeding among critically ill patients, the risk factors for patient-important upper gastrointestinal bleeding, as defined by ICU survivors and family members, are unknown. Further, although trials show that stress ulcer prophylaxis with pantoprazole decreases the risk of upper gastrointestinal bleeding, some research suggests that mortality may be increased among patients with high illness severity who are exposed to pantoprazole. The risk of death during critical illness is greater than the risk of upper gastrointestinal bleeding.

Objective: To identify risk factors for patient-important upper gastrointestinal bleeding among invasively ventilated critically ill adults, taking into account illness severity and the competing risk of death.

Materials and Methods: This pre-planned secondary analysis of the REVISE trial database will be guided by this protocol. We will use Cox proportional hazards regression analysis to assess the effect of candidate risk factors on the hazard rate of the primary outcome of time to patient-important upper gastrointestinal bleeding, considering the competing risk of death. We propose 2 sensitivity analyses. Secondary analyses will evaluate risk factors for clinically-important upper gastrointestinal bleeding, and another model will evaluate whether enteral nutrition attenuates the effect of pantoprazole on bleeding prevention compared to placebo by including an interaction term between pantoprazole vs. placebo and amount of enteral nutrition received.

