We will include both baseline variables and time-dependent variables, described further below. All time-dependent risk factors will be defined as existing any time in the preceding 3 days, but not including the day of bleed. For bleeds that occur on day 1 of the study, we will use day 1 data to define the time-dependent covariates. We will consider ICU discharge and consent withdrawal as censoring events.

Dependent Variables:

Primary Outcome

The primary dependent variable will be patient-important upper gastrointestinal bleeding. This was defined in a mixed-methods study of ICU survivors and families [21], with gastrointestinal bleeding judged as important if bleeding resulted in a blood transfusion, vasopressor treatment, diagnostic endoscopy, CT-angiography, surgery, or if it resulted in death, disability, or prolonged hospitalization [10]. These criteria were applied to the REVISE database up to 90 days after randomization [11]. Our main analysis will include all patient-important upper gastrointestinal bleeds that occurred in the ICU.

Among 4,821 patients, 136 (2.8%) had patient-important upper gastrointestinal bleeding, 5 of whom bled on the ward prompting ICU readmission. These 5 patients will be censored at ICU discharge, as daily data for the time-dependent risk factors were not collected beyond the index ICU admission.

Secondary Outcome

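### The only check on the exposure window moves closer to the bleed, so it cannot show whether low enteral nutrition preceded a bleed or was a response to it

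*Combined protocol and SAP*

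**What the plan says.** Materials and Methods, Risk Factor Analysis, sets the main window: "All time-dependent risk factors will be defined as existing any time in the preceding 3 days, but not including the day of bleed". One exception follows: "For bleeds that occur on day 1 of the study, we will use day 1 data to define the time-dependent covariates". No use of exposure data from before day 1 is described.

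The Abstract announces the robustness work: "We propose 2 sensitivity analyses". Item 1 concerns death: "To evaluate the effect of the competing risk of death, we will conduct an analysis that does not consider the competing risk of death". Item 2 is the only one about the window: "we will evaluate all time-dependent risk factors defined as any time in the preceding 2 days, instead of the preceding 3 days". Its stated purpose is "To evaluate the influence of risk factors more proximate to the bleed".

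Two other places bear on the point. The Discussion says of overt bleeding that "if it evolves into patient-important or clinically-important upper gastrointestinal bleeding, these events will be included in this analysis", so the plan accepts that visible bleeding can come before a qualifying event. Missing Data says of platelet aggregation inhibitors after day 14 that "we will impute that it was continued until ICU discharge, except in the event of bleeding", so it also accepts that care changes when a patient bleeds.

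The plan does not define the day of bleed as either the first overt bleeding or the day a criterion was met. It gives no rule for summarising enteral nutrition, a continuous variable in mL/day, over a window of several days.

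**The concern.** If some bleeds are visible, or suspected, before the recorded day of bleed, clinicians may act on them. Feeds may be reduced or held on the day before. That day is inside both planned windows, so a response to the bleed would be analysed as a preceding exposure. Low enteral nutrition would then look like a risk factor, and higher volume would look protective, even with no true effect.

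This touches a main question of the study. The Discussion presents feeding volume as one of the open issues to be addressed, and Secondary Analyses, item 2, tests whether it changes the effect of pantoprazole. Close agreement between the 3-day and 2-day results would probably be read as robustness, although both carry the same suspect day and part of the agreement is built in.

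**Working it through.** **Event count.** 136/4,821 = 2.82%, which reproduces the stated 2.8%. Removing the 5 ward bleeds leaves 136 - 5 = 131 in-ICU events. The plan gives no figure for the windows themselves.

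**Days in each window.** For a bleed on day t, the main window is days max(1, t-3) to t-1, the check is max(1, t-2) to t-1, and day 1 uses day 1. The lagged window is t-4 to t-2, as available.

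| Bleed day | 3-day | 2-day | Lagged |
|---|---|---|---|
| 1 | 1 | 1 | none |
| 2 | 1 | 1 | none |
| 3 | 1, 2 | 1, 2 | 1 |
| 4 | 1, 2, 3 | 2, 3 | 1, 2 |
| 5 | 2, 3, 4 | 3, 4 | 1, 2, 3 |

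The planned windows are identical through day 3, for cases and for patients still at risk. From day 4 the check drops only t-3, so t-1 goes from 1/3 to 1/2 of the window. This takes the day-1 rule to mean that no earlier data are used. If day-0 data were used, the windows would already differ on day 3 (0, 1, 2 against 1, 2).

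**Enteral nutrition (illustration).** Assume a steady volume V, feeds fully held on t-1, and a window mean as the summary.
- Bleed on day 2: 0 in both planned windows.
- Bleed on day 3: (V + 0)/2 = V/2 in both.
- Bleed on day 4 or later: 3-day (V + V + 0)/3 = 2V/3; 2-day (V + 0)/2 = V/2; lagged V.

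If the summary were the window maximum, the result from day 3 on would be V in every window and the hold would not show. The size therefore depends on a rule the plan does not give.

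**Binary factors: how far the windows can disagree.** From day 4 a binary factor changes class only if present on t-3 and absent on t-2 and t-1. With daily stop probability s, start probability a and steady prevalence p = a/(a + s), the share of 3-day-exposed patients who change class is p·s·(1-a) / [1 - (1-p)(1-a)²].
- s = 0.1, a = 0.02: 0.0163/0.1997 = 8%.
- s = 0.2, a = 0.05: 0.0380/0.2780 = 14%.
- s = 0.3, a = 0.05: 0.0407/0.2264 = 18%.

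The rates are assumptions, and the result does not apply to nutrition volume.

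**Direction of bias (simulation, generic binary exposure).** Assumptions: true ratio 1.0, 400,000 patients, 30% prevalence, 85% daily persistence, daily bleed probability 0.002, bleeds on days 5 to 14, day-stratified Mantel-Haenszel rate ratio. A share q of bleeders is set to exposed on t-1.

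| q | 3-day | 2-day | Lagged |
|---|---|---|---|
| 0 | 1.00 | 0.98 | 1.01 |
| 10% | 1.29 | 1.33 | 0.99 |
| 20% | 1.66 | 1.72 | 1.00 |
| 30% | 2.14 | 2.28 | 1.00 |
| 50% | 3.78 | 4.08 | 1.02 |

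When the exposure is instead stopped on t-1 for 10% to 50% of bleeders, the ratios are 0.93 to 1.00 (3-day), 0.90 to 1.01 (2-day) and 0.96 to 1.03 (lagged). Any-time coding largely hides a stopped binary drug, because earlier days still count. The table shows that the two planned windows share the bias and the lagged one removes it. It does not estimate the bias in this trial.

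**The case against.** **Vasopressors.** A reader might infer that circulatory failure will appear as a risk factor because vasopressors were started for early bleeding. The documents do not support that in general. Vasopressor treatment resulting from the bleed is a criterion for patient-important bleeding, and vasopressor initiation within 24 hours is one for clinically-important bleeding. Starting one for visible bleeding would usually make that day the day of bleed, which is excluded after day 1. What remains is use for bleeding not yet recognised, which is narrower and cannot be sized. This objection stands.

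**Dating of the bleed.** If the day of bleed already means the first overt bleeding, responses to visible bleeding are outside the window. For the clinically-important outcome the accompanying criterion falls within 24 hours, so any delay is short. This stands as a limit on size. It does not remove the point, because the plan does not give the dating rule, and its patient-important criteria carry no time limit.

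**An empty check.** A reader might also infer that item 2 tests almost nothing. That is not shown: the timing of bleeds is not given, and for nutrition volume under a mean or total the windows would differ for most fed patients from day 4. Item 2 is also offered as a look at more proximate factors, not as a test of reverse causation. It serves that purpose; the gap is that no other analysis covers this one.

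**Protection already present.** The bleed day is excluded, the analyses are called exploratory, and the Discussion warns about confounding and association. These help, but none names or tests exposures changed in response to bleeding.

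**Precision.** With 131 events and a binary factor at 50% prevalence, the 95% limits lie a factor exp(1.96 × √(4/131)) ≈ 1.41 either side of the estimate. A modest bias could sit inside that, and a lagged comparison may not be decisive. That is a reason for careful reading, not for omitting the comparison.

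**Conclusion.** The point holds in a limited form. The main window excludes only the day of bleed. The one window check keeps the day before, weights it more heavily from day 4, and matches the main window through day 3. It cannot tell a risk factor from an exposure altered by a developing bleed.

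The concern is mainly enteral nutrition volume. The pantoprazole interaction uses the same variable; it would be distorted if feeds held before the bleed were more common in one arm than the other, which the documents do not address. The concern is weaker for vasopressors and weaker still for binary drugs that are stopped.

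The size is unknown. It depends on how bleeds were dated, how often feeds were changed beforehand, how nutrition is summarised over the window, and how many of the 131 events fall on days 1 to 3. None of these is stated. The main analysis is not shown to be wrong; a plausible alternative explanation for one of its principal results goes untested.

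**What to change.** Add one lagged sensitivity analysis:
- Define time-dependent exposures over days -4 to -2, as available, leaving out the day before as well as the day of bleed, for cases and patients at risk alike.
- Refit the 3-day main model on the same risk set, for example from day 4 on, so that a difference is not due to losing early bleeds.
- Report the two side by side, for enteral nutrition and its interaction with pantoprazole in particular.
- State how mL/day is summarised over a window.
- Date the bleed from the first overt bleeding of the episode where recorded, and otherwise say which date is used.

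The cost is two extra fits for the main model, the same pair with the interaction term, and a few lines of SAP text. The fits use daily data already planned for the analysis; whether the onset of overt bleeding was recorded needs checking. The downsides are older exposure information and loss of the earliest bleeds from this fit. A one-day lag also does not cover changes made two or more days ahead. Attenuation under the lag could reflect genuine short-latency effects as well as reverse causation, so it should be read as a sensitivity result only.
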